2.5 Interim Analysis

No interim analysis is planned for the study.

2.6 Study Procedure

Study procedures and their timing are summarized in the "Schedule of Activities" Table below.

Table 3. Schedule of Activities

Procedure	Baseline	Spinal Procedure	Follow-Up Visit ² 10 days (± 3 days) post spinal procedure
Informed consent process, incl. Informed consent signature date	X		
Inclusion and exclusion criteria	X		
Baseline assessment and Demography	X		
Limited Medical history	X		
Spinal procedure intervention		X	
Ease of use procedure survey		X	
Adverse Event monitoring and assessment ¹		=====	
Serious Adverse Event monitoring and assessment		=====	
Device deficiencies monitoring and assessment		=====	

THIS SUBJECT MATTER IS RESTRICTED SOLELY FOR THE USE OF BECTON DICKINSON AND COMPANY AND ITS SUBSIDIARIES

 BD	Statistical Analysis Plan	Page No.
	Study ID: MDS-21NRFit001	Version No: 1.0

GFM-10082C

¹ Participants will be monitored as required for their routine medical care and according to the hospital policy. Any adverse event or complication must be diagnosed and assessed by a study clinician.

² If the participant has been discharged from the hospital prior to day-10 (± 3 days) post-procedure, follow-up may be performed in a variety of ways including by telephone. The time window of ± 3 days must be used when the 10-day post-procedure occurs during the weekends or holidays. However, any adverse event or complication must be diagnosed and assessed by a study clinician.

3.0 INTENDED STATISTICAL SOFTWARE AND DATA INFORMATION

3.1 Intended Statistical Software

All the analyses will be performed using Statistical Analysis System (SAS) Version 9.4 or above or R.

3.2 Data Information

The input data will consist in several SAS files prepared by the Statistical Programming group and saved in H:\MDS\MDS-21NRFit001\Final\Data on SAS server.

4.0 ANALYSIS POPULATION SET(S)

4.1 Populations Definitions

The following populations are defined in the table below:

Table 4. Population Definitions

Population	Description
Enrolled	All participants who sign the ICF
Treated	All participants in whom a spinal anesthesia procedure is attempted, regardless of success
Safety	All participants in whom a spinal anesthesia procedure is successful

Treated population will include the following participants on the Spinal Procedure CRF page:

- 'Was spinal procedure performed or attempted using BD NRFit devices?' Equals 'Yes'.

Safety population will include the following participants on the Spinal Procedure Details - BD NRFit Needle CRF page:

- 'Was there a spontaneous appearance of cerebrospinal fluid (CSF) emerging from the needle hub?' Equals 'Yes'.

The primary performance endpoints analysis will be performed on the treated population. The primary safety endpoint analysis for PDPH incidence will be performed on the safety population. The primary safety endpoint analysis for device/procedure-related adverse events (other than PDPH) will be performed on the treated population.

THIS SUBJECT MATTER IS RESTRICTED SOLELY FOR THE USE OF BECTON DICKINSON AND COMPANY AND ITS SUBSIDIARIES

 BD	Statistical Analysis Plan	Page No.
	Study ID: MDS-21NRFit001	7 of 13

GFM-10082C

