
 
•anterior spinal artery syndrome,
 
•acute neuropathic pain,
 
•damage to CNS blood vessels,
 
•AV fistula formation,
 
•spinal cord ischemia,
 
•permanent neurological injury,
 
•paraplegia,
 
•hypotension,
 
•cardiovascular collapse,
 
•death.
 
		NRFit™ needles and in the BD Spinal NRFit™ Sets IFUs. See device specific IFU for additional information.
Study Intervention (s): BD Spinal Introducer NRFit™ Needle		

Complications vary based upon anatomic site and clinician experience and may include:
 
 
•localized/systemic infection,
 
•exposure to bodily fluids and/or bloodborne pathogens,
 
•low back pain,
 
•accidental puncture of the dura,
 
•post dural puncture headache.
 
	
A benefit-risk assessment for the overall medical device is documented in the Risk Management Report. All risks and combinations of risks were reviewed, and it has been determined that all are within acceptable limits. The benefits of the device outweigh each risk individually as well as any combination of risk and are consistent with the use of the devices. Therefore, the devices are considered safe for their intended use. These risks are identified as residual risks and are disclosed to the end user.
	
Only physicians experienced in performing procedures using Spinal Introducer Needles should perform neuraxial anesthesia procedures. A caution statement, “To be used by properly qualified and trained healthcare professionals”, is included in the BD Spinal Introducer NRFit™ needle IFU. See device specific IFU for additional information.

Study Intervention (s): BD Syringes NRFit™		

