### 10.3 Analysis Population

The following populations are defined:

Population	Description
Enrolled	All participants who sign the ICF
Treated	All participants in whom a spinal anesthesia procedure is attempted, regardless of success
Safety	All participants in whom a spinal anesthesia procedure is successful

The primary performance endpoints analysis will be performed on the treated population. The primary safety endpoint analysis for PDPH incidence will be performed on the safety population. The primary safety endpoint analysis for device/procedure-related adverse events (other than PDPH) will be performed on the treated population.

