5.2.2 Primary Safety Endpoints

- Incidence of post dural puncture headache (PDPH)

The event of PDPH is defined as headache that worsens when standing/upright position and relieves when laying supine for a period of up to 10 (\pm 3 days) days following the procedure.

The incidence of PDPH will be based on response to the following question:

- "Post-dural Puncture Headache" CRF page: "Did the subject develop post-dural puncture headache (PDPH)?" Equals 'Yes'

Participants experiencing any severity (mild/moderate/severe) of PDPH will contribute to the incidence count in the numerator.

The incidence rate for the above primary safety endpoints will be calculated as the number of participants experiencing the event divided by the total number of safety participants defined in section 4.1; 95% confidence interval (exact method) will be calculated.

- Incidence of any BD NRFit™ spinal needle and BD NRFit™ introducer and BD NRFit™ syringe and procedure-related adverse events (other than PDPH)

Subject will be considered as having an event if the subject has the following responses for the questions on the AE CRF Page listed below:

THIS SUBJECT MATTER IS RESTRICTED SOLELY FOR THE USE OF BECTON DICKINSON AND COMPANY AND ITS SUBSIDIARIES

 BD	Statistical Analysis Plan	Page No.
	Study ID: MDS-21NRFit001	10 of 13

GFM-10082C

- Relationship to procedure: Equals 'Possible' or 'Probable' or 'Causal' OR
Relationship to spinal needle: Equals 'Possible' or 'Probable' or 'Causal'
OR Relationship to syringe: Equals 'Possible' or 'Probable' or 'Causal' OR
Relationship to introducer: Equals 'Possible' or 'Probable' or 'Causal'

The incidence rate for the above primary safety endpoints will be calculated as the number of participants experiencing the event divided by the total number of treated participants; 95% confidence interval (exact method) will be calculated.

THIS SUBJECT MATTER IS RESTRICTED SOLELY FOR THE USE OF BECTON DICKINSON AND COMPANY AND ITS SUBSIDIARIES

 BD	Statistical Analysis Plan	Page No.
	Study ID: MDS-21NRFit001	11 of 13

GFM-10082C

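### PDPH is estimated only in participants with spontaneous CSF at the hub, so a PDPH after a puncture without CSF is left out of the rate judged against 3%

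*SAP*

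**What the plan says.** Protocol 10.3 and SAP 4.1 define two analysis sets beyond the enrolled one. Treated is "All participants in whom a spinal anesthesia procedure is attempted, regardless of success". Safety is "All participants in whom a spinal anesthesia procedure is successful". SAP 4.1 implements the second through one CRF item: "Was there a spontaneous appearance of cerebrospinal fluid (CSF) emerging from the needle hub?' Equals 'Yes". SAP 5.2.1.1 uses the same item to count successful needle placement.

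PDPH is assigned to the smaller set ("The primary safety endpoint analysis for PDPH incidence will be performed on the safety population"), and SAP 5.2.2 gives its denominator as "the total number of safety participants defined in section 4.1". Protocol 10.5.2 agrees. For the second primary safety endpoint, SAP 4.1 says that the analysis for "device/procedure-related adverse events (other than PDPH) will be performed on the treated population".

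The exclusion of PDPH from that second endpoint is not carried through everywhere. It stands in the population statements (Protocol 10.3, SAP 4.1), in the stated objective, and in the endpoint heading of Protocol 10.5.2 and SAP 5.2.2. It is absent from the endpoint columns of the Protocol synopsis, Protocol 3 and SAP Table 1. It is also absent from the SAP 5.2.2 event rule, which counts any AE rated possible, probable or causal for the procedure, needle, syringe or introducer.

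**The concern.** The hazard behind PDPH is a hole in the dura. Protocol 7.4.1 attributes the headache to CSF leaking through that puncture, not to CSF being seen at the hub. Protocol 2.3.1 lists "accidental puncture of the dura" and PDPH among the complications of the spinal needle and, separately, of the introducer. Protocol 7.3.1 foresees several needles and interspaces in one participant, with reasons for failure recorded. A participant with a punctured dura and a CSF answer of No is therefore foreseeable from the documents.

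If that participant develops PDPH, no rule brings the event into the PDPH rate. The main safety rate is then conditioned on the device having performed, and the participants left out are those with unsuccessful placement. At this sample size one case can decide whether the observed rate meets the 3% criterion.

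**Working it through.** **Inputs.** Minimum treated N = 150 (Protocol 4.1, SAP 2.1). PDPH criterion ≤ 3% and placement criterion ≥ 90% (SAP 1.3). Two-sided exact 95% CI (SAP 5.2.2). Precision row: N = 150, rate 3%, half width 3.1% (Protocol Table 1, SAP Table 2). The placement rate that will occur, and the PDPH rate among placement failures, are not given; the values used for them below are assumptions.

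**1. The plan's own figure.** Exact (Clopper-Pearson) limits at n = 150 and x = 0.03 × 150 = 4.5 lie 2.09 points below and 4.15 points above 3%. Half width = (2.09 + 4.15)/2 = 3.12%, which reproduces the stated 3.1%. That row uses 150, the treated minimum, not the CSF-positive number. At n = 135 the same formula gives 3.32%.

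**2. Exclusions by assumed placement rate.** Excluded f = 150 − n. The largest count that meets 3% is the integer part of 0.03n. The chance that at least one PDPH is omitted is 1 − (1 − q)^f, with q the assumed PDPH rate among those excluded.

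| Placement | CSF-positive n | Excluded f | Half width at 3% | Largest passing count | Chance of omission, q = 1% / 3% / 10% |
|---|---|---|---|---|---|
| 90% | 135 | 15 | 3.32% | 4 (2.96%) | 14.0% / 36.7% / 79.4% |
| 95% | 142 | 8 | 3.22% | 4 (2.82%) | 7.7% / 21.6% / 57.0% |
| 98% | 147 | 3 | 3.16% | 4 (2.72%) | 3.0% / 8.7% / 27.1% |

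**3. Effect on the comparison with 3%, at 90% placement.**

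- Planned rate with 4 cases: 4/135 = 2.96% (95% CI 0.81 to 7.41), meets the criterion.
- Treated rate with one further case among the 15 excluded: 5/150 = 3.33% (1.09 to 7.61), does not.
- Treated rate with no case among the 15: 4/150 = 2.67% (0.73 to 6.69), meets it and is lower than the planned rate.

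At 95% and 98% placement the largest passing count is again 4, so one omitted case again gives 5/150 = 3.33% in the treated set.

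**4. Direction.** With a cases among n CSF-positive and b among f excluded, the planned rate a/n is below the treated rate (a + b)/(n + f) exactly when b/f > a/n. If b ≥ 1 and f ≤ 15, then b/f ≥ 1/15 = 6.7%. So, with at most 15 excluded, a planned rate at or below 3% is too low whenever a case has been omitted. If b = 0 and a > 0, it is above the treated rate.

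**The case against.** The restriction has a rationale. PDPH needs a dural puncture, visible CSF confirms one, and the treated denominator includes people whose dura was never reached. The choice is prespecified and the Protocol and SAP agree on it. Using the treated set can also turn a miss into a pass: assuming 180 treated and 90% placement, 5/162 = 3.09% misses 3% while 5/180 = 2.78% meets it. This stands as a reason to keep the CSF-positive rate. It does not justify a numerator that omits a PDPH which did occur.

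Several stronger readings are tempting, but the documents do not support them:

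- *The bias always favours the device.* It does so only when a case is omitted; otherwise the smaller denominator raises the rate.
- *The event disappears from the report.* SAP 7.0 tabulates AEs in the treated population and SAP 6.7 summarises follow-up there. A PDPH recorded as an AE would be visible, though not in the rate judged against 3%.
- *It certainly enters neither primary rate.* The heading, "procedure-related adverse events (other than PDPH"), and the population statement say so, but the event rule beneath that heading has no PDPH filter. The text is ambiguous.
- *Fifteen exclusions are expected.* 90% is an acceptance floor, not a forecast. The last-attempt rule is stated for placement success and not for the Safety set, so CSF on an earlier attempt may qualify a participant and the number excluded may be smaller.
- *Participants with CSF obtained only by aspiration are a known excluded group.* The documents do not describe that situation.
- *The Protocol and SAP define different Safety sets.* SAP Table 4 repeats the Protocol definition, and the CRF rule matches the Protocol's own definition of successful placement.

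**Conclusion.** The gap is real. A PDPH in a treated participant without spontaneous CSF does not enter the rate compared with 3% and, by the endpoint heading and population statement, is not in the other primary safety rate. The endpoint columns and the relatedness rule say otherwise by omission and must be reconciled with them.

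The size depends on the number of placement failures and on PDPH among them, neither of which the documents give; if failures are rare, the effect is small. The comparison with 3% is descriptive: SAP 1.3 asks whether observed data are in line with the literature, and no hypothesis is tested. What is at stake is whether one observed rate lands above or below a threshold, and a single omitted case can settle that at every placement rate examined from 90% to 98%. The loss of precision is minor: 3.3% at 135 against the stated 3.1%.

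**What to change.** Before database lock, in SAP 4.1 and 5.2.2 and Protocol 10.3 and 10.5.2:

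1. Estimate PDPH in the treated population with the exact 95% CI, counting every PDPH in a treated participant.
2. Name this single rate as the one judged against 3%. Asking that two rates both be considered would leave no rule when they disagree.
3. Report the CSF-positive rate as supportive, and state which attempt determines membership of that set.
4. Rename that set, for example as the successful placement set, so that it is not called Safety.
5. State the PDPH exclusion the same way in the endpoint columns, the heading and the event rule of the second safety endpoint. Once PDPH is counted in all treated participants, excluding it there loses nothing.

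The cost is wording in two documents and one table row. Protocol 7.4 follows participants regardless of placement success, so no new data appear to be needed, and the N = 150 precision row then matches its denominator. The downside is that participants whose dura was never reached can lower the treated rate; the supportive CSF-positive rate shows by how much.

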5.0 STATISTICAL ANALYSIS / CALCULATIONS

5.1 Derived Variables

None.

5.2 Analysis Methods

5.2.1 Primary Performance Endpoints

5.2.1.1 Performance of the BD Spinal NRFit™ Needle and BD NRFit™ Introducer

- Rate of successful BD Spinal NRFit™ Needle placement

The successful placement of the BD Spinal NRFit™ needle in the subarachnoid location is defined as the spontaneous appearance of cerebrospinal fluid (CSF) emerging from the spinal needle hub. In case of multiple attempts, successful placement is determined by the last attempt.

It will be computed as the number of participants experiencing the event divided by the total number of subjects with needles attempted; 95% confidence interval (exact method) will be calculated. The analysis will be performed on the treated population as defined in section 4.1.

The incidence of successful needle placement will be based on counts of "Yes" response to the following question on the "Spinal Procedure Details - BD NRFit Needle" CRF page: "Was there a spontaneous appearance of cerebrospinal fluid (CSF) emerging from the needle hub?"

- Rate of successful BD Spinal NRFit™ Needle placement when a BD Spinal NRFit™ Introducer is used

The successful placement of the BD Spinal NRFit™ needle in the subarachnoid location is defined as the spontaneous appearance of cerebrospinal fluid (CSF) emerging from the spinal needle hub for subjects who used BD NRFit™ introducer. In case of multiple attempts, successful placement is determined by the last attempt. If a subject uses BD NRFit™ introducer for the last attempt, the subject will be considered as part of the introducer population.

The incidence rate for the primary performance endpoints will be calculated as the number of participants experiencing the event divided by the total number of treated participants using BD NRFit™ introducer; 95% confidence interval (exact method) will be calculated.

A subject will be included in the analysis population if both of the following two conditions are met:

- Spinal Procedure CRF page: 'Was spinal procedure performed or attempted using BD NRFit devices?' Equals 'Yes'

THIS SUBJECT MATTER IS RESTRICTED SOLELY FOR THE USE OF BECTON DICKINSON AND COMPANY AND ITS SUBSIDIARIES

 BD	Statistical Analysis Plan	Page No.
	Study ID: MDS-21NRFit001	8 of 13

GFM-10082C

- AND
- 'Device Used' Equals 'BD Spinal NRFit Needle Set' OR ('Device Used' Equals 'BD Spinal NRFit Needle' AND 'Was a BD NRFit introducer used?' Equals 'Yes') OR ('Device Used' Equals 'Same as previous attempt' AND either of the previous two conditions is met)

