# 6 STUDY INTERVENTIONS

## 6.1 Investigational/Test Device

The BD Spinal NRFit™ Needles (BD Quincke Spinal NRFit™ Needle and BD Whitacre Spinal NRFit™ Needle) are intended to gain entry into or puncture the spinal cavity permitting injection (including anesthesia) / withdrawal of fluids for purposes of diagnostic lumbar puncture and myelography procedures. They consist of a needle, stylet, and needle shield and are available in various gauges and needle lengths. The needle consists of a hollow needle (cannula) bonded to a translucent hub at one end and a specific needle point type (Quincke or Whitacre) at the other end. The stylet has a handle which is color coded and correlates to the gauge size.

The BD Spinal Introducer NRFit™ Needle is intended for placement or introduction of spinal needles. The BD Spinal Introducer NRFit™ Needle consists of a needle, needle hub and needle shield and is available in various gauges. The needle consists of a hollow needle (cannula) bonded to a translucent colored hub (per gauge) at one end and a specific needle point type at the other end. The introducer needle is an optional aid through which a spinal needle can be inserted.

The needle hub of the BD Spinal NRFit™ Needles and the BD Spinal Introducer NRFit™ Needle incorporates ISO 80369-6 compliant connectors. The needle shields are yellow to

indicate that the devices are intended to only connect to ISO 80369-6 (NRFit™) compatible devices such as syringes.

The BD Spinal NRFit™ Needles and the BD Spinal Introducer NRFit™ Needle are sterile, non-toxic and non-pyrogenic. These products are not made with natural rubber latex, Bisphenol A (BPA) or Di-ethylhexyl Phthalate (DEHP).

The BD Spinal NRFit™ Needles and the BD Spinal Introducer NRFit™ Needle are to be used by properly qualified and trained healthcare professionals.

The BD Spinal NRFit™ Needle Sets (BD Quincke Spinal NRFit™ Needle Set and BD Whitacre Spinal NRFit™ Needle Set) consist of either a BD Quincke Spinal NRFit™ Needle or a BD Whitacre Spinal NRFit™ Needle and a BD Spinal Introducer NRFit™ Needle. The indications for use, populations for which the devices are intended, and materials remain the same of those for the BD Spinal NRFit™ Needles and the BD Spinal Introducers NRFit™ Needles.

The BD Syringes NRFit™ (BD Syringe NRFit™ Lok and BD Syringe NRFit™ Slip) are intended for transient use, intended for neuraxial use by healthcare professionals for aspiration/injection of fluids.

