#### 7.3.1 Spinal procedure data

Information about the spinal procedure will be documented, including, but not limited to:

- Date and time of NRFit™ Introducer/spinal needle insertion
- Participant position (e.g., lateral position, sitting position)
- Aseptic technique
- Preparation anesthetic medication procedure (e.g., accessories used, including Blunt Fill and Blunt Filter NRFit™ Needles)
- Local anesthetic medication used for local skin anesthesia
- Lumbar Interspace selected for the procedure\*
- Spinal NRFit™ Needle type, gauge, length, catalog number, expire date and lot number

- Spinal NRFit™ Introducer, gauge, length, catalog number, expire date and lot number (if used)
- Syringes NRFit™ type, size, catalog number, expire date and lot number
- Spinal NRFit™ set type, gauge, length, catalog number, expire date and lot number
- Number of spinal needles\*
- Lumbar level at which spinal needle placement was successful
- Medications/agents injected (type, dose, volume)
- Maximum spinal block level measured (left and right) (if performed)
- Adverse events/complications (including but not limited to study endpoints)
- Device deficiencies/failures

\* Physicians performing the spinal procedure may use more than one spinal NRFit™ needle. One reason could be a failure with the device, but frequently it is due to the fact that another spinal NRFit™ needle with a different size may be more suitable for that particular participant, due to an individual participant anatomy for example. In this second case, there is no device failure, just the clinician's preference to use a different needle to achieve procedural success.

Information about the different spinal NRFit™ needles (type, gauge, and length) utilized with the corresponding different interspace levels used during the spinal procedure will be also collected with the reason of failure.

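### The introducer success rate drops participants who fail through the introducer and finish without it, and no success rate among all introducer users is planned (minor)

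*SAP*

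**What the plan says.** Protocol 10.5.1.1 and SAP 5.2.1.1 give the same two rules for the introducer endpoint. Membership: "If a subject uses BD NRFit™ introducer for the last attempt, the subject will be considered as part of the introducer population". Outcome: "In case of multiple attempts, successful placement is determined by the last attempt". The SAP divides by treated participants using the introducer and plans an exact 95% interval.

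SAP 5.2.1.1 then turns membership into a CRF condition. A participant qualifies if the device used was a needle set, or a spinal needle with the introducer question answered yes. A third branch covers a device recorded as "Same as previous attempt", "AND either of the previous two conditions is met". The condition does not say which attempt's record is tested.

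Two protocol statements make a change of approach within one procedure possible. In Section 6.1, "The introducer needle is an optional aid through which a spinal needle can be inserted". In Section 7.3.1, clinicians "may use more than one spinal NRFit™ needle". That section also says that a change made because another needle suits the participant better is not a failure: "In this second case, there is no device failure". Details of the needles and interspaces used "will be also collected with the reason of failure".

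**The concern.** The introducer population is chosen partly by what happened after the introducer was tried. Someone who fails through the introducer and stays with it counts as a failure. Someone who fails through it and then abandons it is not counted at all. The rate therefore describes placement on final attempts made with the introducer. It does not describe how often CSF was obtained through the introducer among everyone in whom it was used.

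No other planned output gives that second rate. These participants stay in the overall placement endpoint, but if they reach CSF without the introducer they count there as successes. SAP 6.6 summarises introducer type and names no success rate. SAP 6.8 tabulates and lists device failures and deficiencies, which are counts of problems and not a rate of success among users.

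At stake is the reading of the one primary performance endpoint specific to the introducer, in a study meant to supply clinical data under EU regulation 2017/745.

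**Working it through.** **Inputs from the documents.** About 100 participants treated with the introducer; stated precision 6.0% at a 90% rate; exact 95% interval; placement criterion of at least 90% (SAP 2.4, 5.2.1.1 and 1.3).

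**The plan's own figure.** For n = 100 and p = 0.90, the 95% half width is 1.96 × √(0.9 × 0.1/100) = 5.88% by the simple normal formula, 5.96% by Wilson and 6.36% by the exact method. The stated 6.0% is reproduced by Wilson after rounding. The planned exact interval is slightly wider.

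**Notation.** E = participants in whom the introducer was used on any attempt. S = those with CSF through it. s = those who failed through it and finished without it. a = those with CSF through it who nevertheless finished without it.

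- Planned last-attempt rate: (S − a)/(E − s − a)
- Ever-used rate: S/E

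**Direction.** If CSF ends the attempts, a = 0 and the planned rate is S/(E − s), which is never below S/E. The two are equal when s = 0.

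**Illustration (counts assumed; the documents give none).** E = 100, S = 86, so 14 failures, with s = 5 and a = 0.

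- Last-attempt rate: 86/(100 − 5) = 86/95 = 90.5%, exact 95% CI 82.8-95.6%
- Ever-used rate: 86/100 = 86.0%, exact 95% CI 77.6-92.1%
- Difference: 4.5 percentage points

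With a single switched failure the planned rate is 86/99 = 86.9%, a shift of about 0.9 points.

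**How many switches move the rate to 90%.** With E = 100 and a = 0, the smallest s for which S/(100 − s) is at least 90%:

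| Failures through the introducer | Smallest s | Last-attempt rate | Ever-used rate |
|---|---|---|---|
| 11 | 2 | 89/98 = 90.8% | 89.0% |
| 12 | 3 | 88/97 = 90.7% | 88.0% |
| 13 | 4 | 87/96 = 90.6% | 87.0% |
| 14 | 5 | 86/95 = 90.5% | 86.0% |
| 15 | 6 | 85/94 = 90.4% | 85.0% |

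If S/E is already 90% or more and a = 0, the comparison with 90% does not change.

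**When the direction can reverse.** Protocol 6.1 has the medication given once the CSF flow is judged satisfactory, so some CSF need not end the attempts. With E = 100, S = 90, s = 0 and a = 5, the planned rate is 85/95 = 89.5% against 90/100 = 90.0%.

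**The case against.** The strongest case for the plan is that the rule is prespecified and coherent. Membership and success come from the same attempt, and success follows the same rule as the overall needle endpoint. An ever-used rate answers a different question, and it scores some changes made for anatomy or preference as not successful through the introducer, although Protocol 7.3.1 says such needle changes are not device failures. This stands. It is a reason to keep the planned rate and to add the other beside it.

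Second, the triggering event is hypothetical. Protocol 7.3.1 describes changing the spinal needle, not giving up the introducer. No section describes that switch or gives its frequency. This also stands, and it limits the size of the point.

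Third, some of these cases are visible elsewhere. Protocol 9.6 counts inadequate usability or performance as a device deficiency, including for a device that was tried but not kept through the procedure, and SAP 6.8 lists deficiencies. An introducer dropped for such a reason may therefore appear there. A listing still gives no success rate.

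A reader might also infer two stronger points that the documents do not support.

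- *That the CRF condition could equally be programmed as use on any attempt, giving competing results.* The condition names no attempt, and the membership sentence says if and not only if. But the carry-forward branch is needed only when the record tested is a later attempt that does not itself name its device. Under an any-attempt rule it would be redundant, because the earlier record naming the device already admits the participant. The branch supports the last-attempt reading, so the missing words are a minor clarification.
- *That protocol and SAP conflict on the denominator.* The general sentence in Protocol 10.5.1.1 divides by all treated participants. The same section defines the introducer endpoint for those who used the introducer, and Protocol 10 leaves technical detail to the SAP. No amendment is needed.

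**Conclusion.** The point holds as a minor one. The last-attempt rule removes participants who fail through the introducer and finish without it, and no planned output gives a success rate among all introducer users. The upward direction depends on CSF ending the attempts. The size depends on a switch rate that the documents do not give: nil if nobody switches, about 0.9 points for one switched failure in the illustration, and 4.5 points for five.

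It would go too far to conclude that the introducer would wrongly meet a 90% hurdle. SAP 1.3 frames the criterion as a descriptive comparison with the literature and states it for needle placement. Its use for the introducer is inferred from Protocol 3.1, which names both devices, and from the n = 100 precision row. No test depends on it.

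**What to change.** Change SAP 5.2.1.1 only.

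1. Keep the last-attempt rate, and add to the CRF condition that it is tested on the last attempt.
2. Report beside it a supplementary ever-used rate with an exact 95% interval. The denominator is all treated participants with an introducer or needle set on any attempt. Success requires spontaneous CSF on an attempt made through the introducer.
3. Report the number who finished without the introducer, with the reason where the CRF recorded one.

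The cost is a few lines of SAP text and one derived variable; SAP 5.1 currently lists none. The CRF items quoted in the SAP imply attempt-level device and CSF data, but the CRF itself is not among the documents. Protocol 7.3.1 does not clearly collect a reason for dropping the introducer, so item 3 may be incomplete. The supplementary rate may be lower than the planned one, and it counts some preference or anatomy changes as not successful through the introducer. It should therefore stand beside the last-attempt rate and not replace it.
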